#### **Ethical Considerations**

During the study, participants were free to change their minds and withdraw from the study at any time without penalty. Participants were allowed to refuse treatment on any given day for any reason. During sessions, participants also had the right to leave the study or decline to participate in specific group activities (e.g., warm-up song) without any negative consequences. During evaluation and assessment, participants could skip any questions they did not wish to answer. Whatever the participant decided would not result in any loss of benefits or services to which they were otherwise entitled.

#### **Data Collection and Management**

Data were collected between June and August 2025 using participant ID codes. Names were excluded from data collection sheets, which included only ID codes and initials to prevent

confusion. Physical documents were stored in a password-protected file folder, and digital data sheets are on two encrypted flash drives. Informed consent forms and medical records are secured in the faculty advisor's office in the locked file folder due to identifiable information being present; no identifiable data are stored on flash drives. Access is limited to the research team and faculty advisor. Data will be retained for six years and then paper documents will be shredded and digital storage devices securely wiped.

#### Statistical Analysis Plan

Data were analyzed using IBM SPSS Statistics (Version 29). Demographic characteristics were analyzed using descriptive statistics. Normality of the data was assessed using the Shapiro-Wilk test, which indicated that the majority violated assumptions of parametric testing (Gil et al., 2022). A one-tailed Wilcoxon signed-rank test was conducted to assess pre- and post-intervention outcomes (Gil et al., 2022; Lok et al., 2020). To reduce a Type I error from multiple comparisons, a Bonferroni correction was applied to adjust the significance level to  $p \le .0045$  for the OME-Modified and  $p \le .05$  for the MoCA. Effect sizes (r) were calculated using  $Z/\sqrt{N}$  (0.1 = small effect, 0.3 = medium, 0.5 = large). Confidence intervals for r could not be computed due to sample size and software limitations. Due to the statistical probability of change in subtests, descriptive statistics were used to determine whether the performance in MoCA and OME-Modified subtests increased, decreased, or maintained.

Data inclusion was predetermined at 50% attendance, equivalent to attending at least two-thirds of each session and 7/14 sessions. Participants outside this criterion were classified as dropouts and excluded, with their data removed. This approach ensured that the analysis reflected outcomes from participants who meaningfully engaged in the intervention.

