#### **Study Summary and Objectives**

This research examined the effectiveness of CST while aiming to support and validate the role of occupational therapy and promote its integration into long-term care settings across the United States. Currently, there is limited research on occupational therapists implementing CST with older adults living with dementia in long-term care facilities. The purpose and aims of this research study were to: 1) investigate the preliminary effect of CST on cognition and engagement in individuals with mild-to-moderate dementia, and 2) assess the feasibility of implementing CST in LTC facilities in the Cincinnati metropolitan area. The objective of this research was to answer the following question: Does CST improve cognitive functioning and increase engagement levels in individuals with mild-to-moderate dementia residing in long-term care facilities? We hypothesized that individuals with mild-to-moderate dementia who participated in a 7-week CST program in a long-term care facility would exhibit significantly higher levels of engagement and cognitive functioning compared to baseline.

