#### **Study Procedures**

Before the start of the study, participants underwent a screening measure where they

performed the ADAS-Cog-a neuropsychological test designed to assess the severity of cognitive impairment-to assess for cognitive impairment (Schafer et al., 2013). Another occupational therapy student researcher from the NKU Occupational Therapy program demonstrated competency in administering the ADAS-Cog under the supervision of a licensed occupational therapist prior to conducting the screenings. Participants who scored within the mild-to-moderate range (18–55) on the screening were eligible for admission into the study and proceeded to pretesting. Pre-testing and post-testing were conducted by a different NKU occupational therapy doctoral student, also supervised by a licensed occupational therapist, who had demonstrated competency in administering the Montreal Cognitive Assessment (MoCA) and The Observational Measurement of Engagement-Modified (OME-Modified) to minimize bias. The MoCA and OME-Modified were administered to participants as primary outcome measures to evaluate levels of cognitive impairment and engagement. The MoCA is a standardized tool that assesses cognitive domains: attention, executive functions, short-term and working memory, language, visuospatial, and orientation (Nasreddine, 2017). Scores range from 0 to 30, with scores of 18 to 25 indicating mild impairment, 10 to 17 indicating moderate, and 0 to 9 indicating severe (Nasreddine, 2017). The MoCA was selected due to its sensitivity to changes in cognition (Julayanont et al., 2013).

The OME-Modified assessed engagement through the assessment of a participant's response to a stimulus during an activity, taking note of their attention and attitude using standardized rating scales. The OME-Modified was selected due to its focus on the core outcomes, ease of use in an applied setting, high intra-class correlation value (.78), and high inter-rater reliability (0.84 - 0.92) (Cohen-Mansfield et al., 2010). Participants performed each assessment on alternate days to limit cognitive fatigue.

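### The OME-Modified level of .0045 implies 11 tests that the plan does not identify, and an exact one-tailed signed-rank p cannot reach it with 7 or fewer changed pairs

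*Combined protocol and SAP*

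**What the plan says.** Under Study Procedures, both instruments are primary: "The MoCA and OME-Modified were administered to participants as primary outcome measures". The only OME-Modified content named there is a response to a stimulus, "taking note of their attention and attitude using standardized rating scales".

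The Statistical Analysis Plan section gives the test: "A one-tailed Wilcoxon signed-rank test was conducted to assess pre- and post-intervention outcomes". It then sets two levels, .0045 for the OME-Modified and .05 for the MoCA, in the sentence that begins "To reduce a Type I error from multiple comparisons, a Bonferroni correction was applied to adjust the significance level to". Effect size comes from the test's Z: "Effect sizes (r) were calculated using" Z/√N. On subtests, "descriptive statistics were used to determine whether the performance in MoCA and OME-Modified subtests increased, decreased, or maintained". On attendance below the criterion, "Participants outside this criterion were classified as dropouts and excluded, with their data removed".

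The Participants section sets the sample size at 10. The hypothesis under Study Summary and Objectives is that participants "would exhibit significantly higher levels of engagement and cognitive functioning compared to baseline".

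The plan gives no number of comparisons, no list of OME-Modified scores to be tested, no error family, no success rule, and no statement of whether p is exact or asymptotic.

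**The concern.** A Bonferroni level is interpretable only if the reader knows which tests it was divided over. Here the reference to multiple comparisons points to several OME-Modified tests, while the subtest sentence points to one. The two readings lead to different problems. With one test, a divisor of 11 has no basis. With 11, each instrument is controlled separately, but nothing is said about error across the two.

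Sample size adds a second difficulty. A signed-rank p-value from a handful of pairs has a floor set by the number of non-zero differences. With at most ten pairs, that floor lies close to .0045. A non-significant OME-Modified result could then reflect the level and the number of changed pairs, and be misread as no change in engagement. In the same range, the choice between exact and normal-approximation p-values can decide the verdict on a primary outcome.

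**Working it through.** **Inputs.** Levels .0045 and .05, one-tailed signed-rank test and r from Z (Statistical Analysis Plan); two primary outcomes (Study Procedures); planned N = 10 (Participants). The numbers analysed and changed are not given, so n, the number of non-zero differences, is shown as a range.

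**1. Reproducing the level.** .05/10 = .0050, .05/11 = .004545, .05/12 = .0042. Only 11 rounds to .0045. The division is right; the count of 11 is what cannot be traced. The MoCA level of .05 corresponds to a divisor of 1.

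**2. Floor of the exact test.** If all n changed pairs improve, the one-tailed exact p is 1/2^n, with or without ties. The third column comes from enumerating the untied null distribution.

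| n changed | smallest exact p | largest negative rank sum with p ≤ .0045 |
|---|---|---|
| 5 | .031 | none |
| 6 | .016 | none |
| 7 | .0078 | none |
| 8 | .0039 | 0 |
| 9 | .0020 | 1 |
| 10 | .00098 | 2 |

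So .0045 needs at least 8 changed pairs, and with exactly 8 all must improve. Since 10 − 3 = 7, three participants excluded or unchanged are enough to put it out of reach. The MoCA's .05 is reachable from n = 5.

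**3. Exact against normal p.** Normal p = Φ(−(n(n+1)/4 − W)/√(Σ rank²/4)), where W is the negative rank sum and there is no continuity correction.

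- n = 7, all changes identical and favourable: (14 − 0)/√28 = 2.646, normal .0041. Exact .0078. Only the normal p passes; with continuity correction it is .0054 and fails.
- n = 8, untied, all improving: (18 − 0)/√51 = 2.521, normal .0059. Exact .0039. Only the exact p passes.
- n = 9, untied, only the smallest change a decline (W = 1): (22.5 − 1)/√71.25 = 2.547, normal .0054. Exact .0039. Only the exact p passes.
- n = 10, untied, W = 2: (27.5 − 2)/√96.25 = 2.599, normal .0047. Exact .0029. Only the exact p passes.

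**4. Error across both instruments, if 11 OME-Modified tests were run.** Within the OME-Modified the sum is 11 × .0045 = .0495, and the MoCA alone is at .05. Nominally, for at least one false claim across the two:

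- independent tests: 1 − .95 × (1 − .0045)^11 = .096;
- upper bound: .05 + 11 × .0045 = .0995.

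Exact tests do not use the full level. The largest attained sizes over all tie patterns at .0045 and .05 are .0039 and .0469 at n = 8, .0039 and .0488 at n = 9, and .0039 and .0498 at n = 10. With the same n in every test, the bound is 11 × the first + the second, taking .0039 as 1/256 = .003906: .090, .092 and .093. At n ≤ 7 no OME-Modified test can reject, so the bound is the MoCA's own size, at most .047.

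**The case against.** The strongest defence is that 11 OME-Modified scores were tested against one MoCA total. That would explain both the reference to multiple comparisons and the undivided MoCA level. The subtest sentence says descriptive statistics were used to classify change; it does not say that nothing else was done. This is plausible, and it is why the point is not that .0045 is an arithmetic error, an inference a reader might draw. What remains is that the 11 tests are not listed and the subtest sentence is not reconciled with them.

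Second, .0045 is reachable at the planned N of 10. This stands. The documents do not report how many were excluded or unchanged, so they do not support a claim that the OME-Modified could not have succeeded. The floor also applies to exact p-values, which the plan does not specify. The use of Z for r suggests a normal approximation may have been used but does not establish it. The n = 7 conflict needs all changes to be identical and no continuity correction.

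Third, treating each instrument as its own error family is defensible in a study of preliminary effect, and the hypothesis joins the two outcomes with an and. If each is its own family, or if both must succeed, the cross-instrument excess disappears. This also stands, but the plan states neither rule. By the same token, a two-outcome split at .025 is not a rule the plan adopted, and its absence is not a fault.

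**Conclusion.** The concern holds in a limited form. The OME-Modified level implies a divisor of 11 that cannot be matched to any tests the plan describes. By exact test it cannot be met with 7 or fewer changed pairs, that is, if three or more of the planned ten are excluded or unchanged. From 7 to 10 changed pairs, the unstated choice of p-value method can reverse the verdict at .0045.

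A reader might infer that the study's error rate is about 10%. The documents do not support that. The nominal .096 assumes 11 independent OME-Modified tests, independence from the MoCA, and success on either instrument alone. The exact-test bounds of .090 to .093 assume equal numbers of changed pairs, at least 8, in every test. Each instrument taken alone stays controlled at .05. The problem should be corrected because the interpretation of a primary outcome depends on it.

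**What to change.** 1. Use exact signed-rank p-values for both outcomes at the original .0045 and .05 levels, and report the number of changed pairs for each test. If the original p-values were asymptotic, show both sets, say which was used originally, and flag any verdict that differs.
2. Name the OME-Modified tests behind the divisor of 11, reconcile them with the subtest sentence, and state the error family and the success rule.
3. Do not read a non-significant OME-Modified result at .0045 as evidence of no change. If either instrument alone counts as success, do not claim 5% error control across both.

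A Holm analysis is optional. It is relevant only if either outcome alone counts as success, and it should be labelled post hoc.

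The cost is some rewording, a small re-analysis (at most 2^10 = 1,024 sign patterns per test) and possibly less favourable claims.

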An occupational therapy student researcher collaborated with staff on-site during the spring of 2025 to review the study information to prepare the staff to identify individuals who meet the inclusion criteria. The student performed recruitment, which involved convenience sampling within the SNF, ALF, and memory care units, contacting the participant and, when applicable, their power of attorney (POA) using approved recruitment scripts, information handouts, and consent forms, in person or by phone. The informed consent forms and participant handout were developed at an 8th-grade reading level to ensure accessibility and understanding for individuals with cognitive impairments or limited health literacy. The POA is an individual who is legally responsible for an individual and was able to provide consent for the study alongside their family member with dementia. Two consent processes were used: a dual consent form for individuals with a POA, requiring signatures from both parties in recognition of the cognitive considerations associated with dementia, and a standard form for those without a POA. Consent was obtained either electronically or in person with physical signatures. All participants and their POAs (if applicable) provided written or verbal reconsent prior to the intervention due

to the study design change. The student repeated this process with multiple participants and POAs until the sample size was achieved. Before recruitment, researchers established a target sample size based on the *CST Making a Difference 1* Manual, which recommends 5 to 8 participants per group. To account for potential variability in attendance due to scheduling conflicts, mood fluctuations, or health-related absences, a sample size of 10 participants (N = 10) was set to help maintain a consistent group size of 5 to 8 participants per session.

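### With 10 or fewer participants analysed, any significant result is a 'large' effect by construction, and the SAP states no MoCA change in points and no interval for one

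*Combined protocol and SAP*

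**What the plan says.** All of the analysis text is in the Statistical Analysis Plan section of the combined document. The test is a one-tailed Wilcoxon signed-rank test, at .05 for the MoCA and .0045 for the OME-Modified. On magnitude it says "Effect sizes (r) were calculated using" Z/√N, with 0.1, 0.3 and 0.5 marking small, medium and large. N is not defined there. On precision it says "Confidence intervals for r could not be computed due to sample size and software limitations".

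The only other outcome summary is for subtests: "descriptive statistics were used to determine whether the performance in MoCA and OME-Modified subtests increased, decreased, or maintained". That gives direction, not amount.

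On size, the Participants section says "a sample size of 10 participants (N = 10) was set" and "The student repeated this process with multiple participants and POAs until the sample size was achieved". The SAP then removes people who fall short on attendance: "Participants outside this criterion were classified as dropouts and excluded, with their data removed". The number analysed is not given. Study Procedures says of the MoCA, "Scores range from 0 to 30", and gives its severity bands in points.

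**The concern.** The first aim in Study Summary and Objectives is a preliminary effect on cognition and engagement. For a small study with no power calculation, the useful output is how big the change was and how uncertain it is.

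For a fixed N, r is the test statistic divided by a constant. The significance threshold therefore sets a floor under r for every significant result. If that floor lies above 0.5, 'large' merely repeats that p was small. A reader, or someone planning a follow-on trial, could take it as a statement about the amount of cognitive gain. The SAP states no quantity in MoCA points that would correct that reading.

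**Working it through.** The documents report no r, no analysed N and no point change, so there is no figure of the plan's own to reproduce. The check is what the stated formula implies.

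**Inputs.** One-tailed test, thresholds .05 and .0045, r = Z/√N and the cut-offs, all from the Statistical Analysis Plan. Target of 10 participants, from Participants.

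**Step 1: floor on r at one-tailed .05, N as participants.** By normal approximation the smallest significant r is 1.645/√N. The exact version enumerates every pattern of ties and zero changes (zeros dropped, average ranks, tie-corrected variance) and takes the smallest r with exact p ≤ .05.

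| N | 1.645/√N | Exact minimum over all patterns |
|---|---|---|
| 5 | .736 | .905 |
| 6 | .672 | .728 |
| 7 | .622 | .640 |
| 8 | .582 | .577 |
| 9 | .548 | .540 |
| 10 | .520 | .507 |
| 11 | .496 | .476 |

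The exact minimum at N = 10 comes from tied groups of 5, 2, 1 and 2. The ranks are 3 (five times), 6.5 (twice), 8, and 9.5 (twice). The sum of squared ranks is 45 + 84.5 + 64 + 180.5 = 374, so the variance is 374/4 = 93.5. With W+ = 43, Z = (43 − 27.5)/√93.5 = 1.603, r = 1.603/√10 = .507 and exact p = .0498.

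Every entry up to N = 10 exceeds 0.5, and N = 11 does not: (1.645/0.5)² = 10.8. At .0045 and N = 10 the floor is higher still: 2.612/√10 = .826 by normal approximation, .790 exact.

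**Step 2: the converse.** With n = 8, no ties and W+ = 29, the mean is 18 and the variance 8·9·17/24 = 51. Then Z = 11/√51 = 1.540 and r = 1.540/√8 = .54, which is 'large'. But p = .074 exact and .062 normal. So the label does not separate significant from non-significant results either.

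**Step 3: r is blind to points (invented data).** Take ten changes: −1 twice, 1 six times, 2 twice. The ranks are 4.5 (eight times) and 9.5 (twice). W+ = 6(4.5) + 2(9.5) = 46 and the variance is (162 + 180.5)/4 = 85.6. Z = 18.5/√85.6 = 2.00, r = .63 and exact p = .036. The Hodges-Lehmann change is 1 point, with the 9th to 47th of 55 pairwise averages running from 0 to 1.5. Triple every change and the ranks, r and p are identical, but the change is 3 points (0 to 4.5).

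**Step 4: can an interval be had at this size?** Inverting the signed-rank test, without ties, the attainable two-sided coverage nearest above 95% is:

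- n = 6: 96.9%
- n = 7: 95.3%
- n = 8: 96.1% (4th to 33rd of 36 averages)
- n = 9: 96.1%
- n = 10: 95.1% (9th to 47th of 55)
- n = 5: not attainable (maximum 93.8%)

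**The case against.** The strongest reply is that r is conventional, the formula and cut-offs are openly declared, and any statistic tied to Z has a high significance floor at 10 participants. That is fair as far as it goes. It argues for keeping r if the authors wish. It does not make the size label informative, and it does not supply a change in points.

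Several stronger readings are tempting, and the documents do not support them:

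- **That the sentence on intervals for r is wrong.** It concerns r only and is not challenged here. The point is that sample size does not prevent an interval for the change itself.
- **That no point change was ever reported.** The documents contain no results. The SAP does not state one, and no more than that can be said.
- **That an OME-Modified total is missing a point estimate.** No section describes such a total. The omission claim is secure only for the MoCA.
- **That N might mean 20 observations.** The MoCA floor would then be 1.645/√20 = .368, 'medium'. But the one place that gives N a value uses it for participants, so this is only a reason to write the definition down.

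It also stands that the analysis is described as already done, and that this addition alters no test, threshold or conclusion about significance.

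**Conclusion.** The concern holds for the SAP as written. With N as participants and 10 or fewer analysed, any result significant at one-tailed .05 has r of at least .507 and is labelled 'large' regardless of points gained; some non-significant results are labelled 'large' too. The SAP states no change in points, and no interval for one, for the MoCA total.

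This rests on two assumptions: that N counts participants, as in the Participants section, and that the target of 10 was not exceeded. At 11 the guarantee fails.

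A reader might also infer that a MoCA interval would measure the effect of CST. It would not. The Methods describe a single group without blinding, and the SAP restricts the analysis to those meeting the attendance rule, so the interval would cover sampling error in pre-post change only. This is a worthwhile reporting improvement, not a flaw that invalidates the test.

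**What to change.** - State that N in Z/√N is the number of pre/post pairs.
- For the MoCA total, report the Hodges-Lehmann change in points with an interval from inverting the signed-rank test, marked as added after the analysis. Say that it equals the median change only if differences are symmetric, and that ties make coverage approximate or conservative.
- Choose the interval knowingly. A two-sided 95% interval can include zero when the one-tailed test is significant (n = 10, no ties: rank sums 45 and 46, p = .042 and .032). The matching one-sided 95% lower limit (11th smallest of 55 averages at n = 10, 6th of 36 at n = 8) or a 90% interval avoids this.
- For the tested OME-Modified outcomes, give any such estimate as descriptive only. Note that the ratings are ordinal, that some post-tests used a different stimulus (Study Procedures), and that the interval is not adjusted to .0045.
- Drop the size labels, or state that at N of 10 or fewer any significant result is 'large' by construction. Keep the existing interval sentence confined to r.
- State that the interval reflects sampling error only, in one uncontrolled, unblinded, attendance-restricted group, and does not estimate the effect of CST.

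**Cost.** A few lines on existing data; at n = 10, 55 pairwise averages can be sorted in a spreadsheet if the software does not produce them. The downside is a wide interval that looks less favourable than 'large effect'. If the SD of MoCA change were 2 to 4 points (an assumption; the documents give none), simulated 95% intervals average about 2.9 to 5.7 points wide at n = 10 and 3.5 to 7 at n = 8.

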#### Methods

A quasi-experimental, single-group pretest-posttest design was used to evaluate the effects of engagement and cognitive functioning in a group CST program. The study was

conducted as a student-led research project by occupational therapy doctoral students from Northern Kentucky University (NKU) who had completed their didactic coursework, including a group intervention course, and their first Level II fieldwork prior to engaging in on-site activities.

Although a randomized controlled trial (RCT) was initially planned, recruitment challenges, time constraints, and logistical limitations led to a modification of the study design. The modification addressed an ethical concern regarding the control group not receiving the intervention, as a delayed intervention was not logistically feasible for the researchers. Due to the nature of the study design, no blinding of participants or researchers occurred. The study was approved by NKU's Institutional Review Board for human subjects research (IRB # 2562) and revisions to the study protocol were approved prior to the start of the intervention. The study was registered at ClinicalTrials.gov (NCT06978972) and made public in June 2025. The study was conducted from May to August 2025 at a long-term care facility in southeast Indiana that provides memory care, assisted living (ALF), and skilled nursing (SNF) care. Data was collected between June and August 2025.

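### The only inferential analysis is confined to participants who met an attendance rule; it answers a question about attenders, and no analysis of all available pre/post pairs is described for the question about residents

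*Combined protocol and SAP*

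**What the plan says.** The Methods section describes one group: "A quasi-experimental, single-group pretest-posttest design was used". The Statistical Analysis Plan names one inferential outcome analysis: "A one-tailed Wilcoxon signed-rank test was conducted to assess pre- and post-intervention outcomes". Demographics and subtests are handled descriptively. The significance levels are .05 for the MoCA and .0045 for the OME-Modified.

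The analysis set is then limited: "Data inclusion was predetermined at 50% attendance, equivalent to attending at least two-thirds of each session and 7/14 sessions". Those outside it are dealt with as follows: "Participants outside this criterion were classified as dropouts and excluded, with their data removed". The reason given is that "This approach ensured that the analysis reflected outcomes from participants who meaningfully engaged in the intervention".

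Other sections bear on this:

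- **Participants** expects variable "attendance due to scheduling conflicts, mood fluctuations, or health-related absences". The enrolment of 10 "was set to help maintain a consistent group size of 5 to 8 participants per session".
- **Ethical Considerations** adds: "Participants were allowed to refuse treatment on any given day for any reason".
- **Study Summary and Objectives** asks whether CST helps residents with mild-to-moderate dementia in long-term care, and lists feasibility as the second aim. The hypothesis is worded for those who took part in the program.
- **Study Procedures** has attendance recorded on the session monitoring forms, and leaves the form data to a future study.

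No section describes an analysis of everyone with both tests, or a report of how many were excluded, why, or with what baseline scores.

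**The concern.** Attendance is observed after the pre-test and may share causes with the outcome. A resident whose health or mood is worsening may miss sessions and also score less well seven weeks later. If so, removing low attenders removes the less favourable changes. With no comparison group, nothing offsets that selection, and it goes straight into the pre/post change. Fixing the cut in advance prevents a data-driven choice of cut but does not break a link between attendance and change.

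What is at stake is whether the result can be read as an answer about residents rather than about those who kept attending. The number below the rule, and the reasons, are also direct evidence on the feasibility aim.

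**Working it through.** **The plan's own figure.** Two sessions a week for 7 weeks is 14, and 7/14 = 50%, so the stated equivalence reproduces. The second condition, two-thirds of each session, has no figure to check. Its wording is unclear, since nobody attending only half the sessions can attend part of every one. It presumably defines when a session counts as attended. It can only add exclusions, and the counts below ignore it.

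**How many might be excluded.** The documents give no count. Ten enrolled for 5 to 8 present suggests 5/10 to 8/10, or 50–80% attendance. This is inferred from a group-size target and is not a forecast in the plan. Expected number excluded = 10 × P(X ≤ 6), where X is sessions attended out of 14:

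| Attendance | Independent absences (binomial) | Absences clustered by person (beta-binomial, assumed ICC .2) |
|---|---|---|
| 80% | 10 × .0024 = 0.02 | 10 × .0819 = 0.82 |
| 65% | 10 × .0753 = 0.75 | 10 × .2341 = 2.34 |
| 50% | 10 × .3953 = 3.95 | 10 × .4529 = 4.53 |

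None, one, or several are all compatible with the plan.

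**Shift in the mean change.** Assume no true mean change in all 10, normal changes, correlation r between attendance and change, and the k lowest attenders removed. The expected three lowest of ten standard normal values are −1.539, −1.001 and −0.656. The shift in SD units is r × (sum of the k lowest, sign reversed)/(10 − k):

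- k = 1: 1.539/9 = 0.171; times .3 and .5 gives 0.05 and 0.09.
- k = 2: 2.540/8 = 0.318; gives 0.10 and 0.16.
- k = 3: 3.196/7 = 0.457; gives 0.14 and 0.23.

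**MoCA rejection at .05.** Same assumptions, no ties, exact one-tailed signed-rank test, by simulation:

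| r | None removed | 1 removed | 2 removed | 3 removed |
|---|---|---|---|---|
| 0 | 4.2% | 4.9% | 3.9% | 3.9% |
| .1 | 4.2% | 5.4% | 4.6% | 4.9% |
| .3 | 4.1% | 6.5% | 6.6% | 7.7% |
| .5 | 4.2% | 8.2% | 9.4% | 11.9% |

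The r = 0 row differs from 5% only because the exact test is discrete. Part of the rise with one removed (4.2% to 4.9%) is that discreteness and not selection. With whole-point changes and zeros dropped, 2–3 removed and r = .3–.5, the rate goes from 4.1% to 6.3–10.9% if the SD of change is 3 points, and from 3.2% to 4.3–7.0% if it is 1.5 points. Both SDs are assumed.

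**The same test with attenders as the target.** Recentre the simulation so that the retained attenders have zero mean change. With 2–3 removed and r = .3–.5, rejection is 4.0–4.3%.

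**OME-Modified at .0045.** The smallest exact one-tailed p with n untied pairs is 1/2^n. That is 1/256 = .0039 for n = 8 and 1/128 = .0078 for n = 7. With 2 removed, rejection is 0.7–1.2% (r = .3–.5). With 3 removed it is impossible. The plan does not say whether exact or normal-approximation p-values were used. By the normal approximation the largest Z at n = 8 is 18/√51 = 2.52, p = .0059, so .0045 is already out of reach with 2 removed.

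**The case against.** The strongest reply is that the plan chose its target. The rule is described as set in advance, its reason is stated, and the hypothesis is about those who participated. For that target the recentred check shows no inflation. This stands. A reader might infer that the reported test has a false-positive rate of up to 12%. The documents do not support that, because the figure counts as errors rejections in which the attenders truly improved on average. It is an error rate only for the question about all residents.

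A second reply is that the larger figures need 2–3 exclusions, while independent absences at 65–80% attendance give fewer than one. This also stands, which is why the one-removed results belong beside the others. Nor should a reader infer that exclusions occurred or were chosen after seeing results; no count is given, and the cut is called predetermined.

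Third, the plan is silent on reporting exclusions and does not forbid it. That is fair, and in a small preliminary study it could be settled in the results. But silence on the count does not supply an analysis of all available pairs. The stated question and the feasibility aim reach beyond attenders.

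Finally, if attendance relates to change because the sessions work, including low attenders dilutes a real dose-related effect. That is a reason to show both analyses.

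**Conclusion.** The concern holds in limited form and should be fixed. The attender analysis is valid for attenders. Alone, it does not answer the question about residents with mild-to-moderate dementia, and for that question it is biased toward improvement if low attenders change less favourably. With an assumed correlation of .3–.5, the shift is 0.05–0.09 SD with one of ten removed and 0.10–0.23 SD with two or three. MoCA rejection is then about 6.5–8% and 6.6–12%, against about 4.2% with none removed. At correlation .1 the shift with two or three removed is 0.03–0.05 SD, and at zero there is no bias. For the OME-Modified the concern is mainly the shifted estimate and the loss of any attainable result at .0045, not false positives.

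The correlation, the number removed, the absence of ties and the exact test are all assumptions. Confidence is medium because the documents fix neither of the first two.

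**What to change.** Add to the Statistical Analysis Plan:

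> Every enrolled participant with both a pre-test and a post-test is analysed regardless of attendance. This analysis was added after data collection and is shown beside the predetermined attendance set, which is labelled per-protocol and whose conclusions are limited to attenders. The number excluded under each condition (fewer than 7 of 14 sessions; less than two-thirds of a session), the reasons, and their baseline scores are reported.

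If excluded participants have no post-test, report the exclusions and limit the conclusion to attenders. If nobody was excluded, one sentence saying so settles the matter.

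The cost is SAP wording, one short table and one extra run per outcome. Data Collection and Management keeps data for six years, but the documents do not show whether anyone excluded was post-tested. The estimate may be less favourable, low attenders may dilute a dose-related effect, and the added analysis is post hoc and still omits anyone without a post-test. It therefore accompanies the predetermined set and does not replace it.
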